	
 Food or beverages containing xanthine derivatives or xanthine-related compounds or energy drinks from 48 hours pre-first dose until study exit Food or beverages containing grapefruit, Seville orange, starfruit, pomegranate, pineapple, or pomelo from 14 days pre-first dose until study exit Alcohol-based products from 24 hours prior to admission until study exit Artificial nails or nail polish at screening and during confinement 
Subjects will be allowed to engage in normal activity throughout the study.
 
Given the long confinement of the study, outings will be permitted during the confinement. Pre-scheduled and supervised outings will also be permitted for smoking subjects during confinement. Outings will be supervised at all times by the clinical staff to ensure compliance with protocol and will be limited to the grounds surrounding the clinic, as per the clinical site-specific procedures for supervised outings.
 
Part 1 (SAD)
 
Subjects will be required to avoid lying down or sleeping, unless medically necessary or procedurally required, for 4 hours after drug administration.
 
Part 2 (MAD)
 
On Days 1, 4, 7, 10, and 13, subjects will be required to avoid lying down or sleeping, unless medically necessary or procedurally required, for 4 hours after morning drug administration.

PK Sample Collection:	
Part 1 (SAD) – Cohorts 1 to 5
 
A total of 11 blood samples will be collected: at pre-dose and 1.5, 3, 5, 7, 9, 12, 24, 36, 48, and 72 hours post-dose.
 
Part 2 (MAD) – Cohort 6
 
On Day 1, a total of 10 blood samples will be collected for quantitation of nalbuphine and metabolite(s) in plasma: at pre-dose and 1.5, 3, 4, 5, 6, 7, 9, 12, and 24 hours post-dose.
 
On Days 4, 7, and 10, a total of 9 blood samples will be collected; at pre-morning dose and 1.5, 3, 4, 5, 6, 7, 9, and 12 hours post-dose (prior to the evening dose administration).
 
On Day 13, a total of 12 blood samples will be collected: at pre-dose and 1.5, 3, 5, 7, 9, 12, 24, 36, 48, 72, and 96 hours post-last dose.
 
Trough blood samples will be collected on Days 2, 3, 5, 6, 8, 9, 11, 12, and 13 prior to the morning and evening dose administrations (if applicable).
 
Plasma samples will be analyzed to determine nalbuphine and M1, M2, M4, and M5 metabolite concentrations using validated assay methods.

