	
and metabolite(s). The 90% confidence intervals (CIs) (Mild/Control, Moderate/Control, and Severe/Control) will be calculated for AUC_{0-t}, AUC_{0-inf}, and C_{max}. For these analytes, T_{max} will be analyzed non-parametrically with point estimates and 90% CIs for the median differences of T_{max} between groups (Mild-Control, Moderate-Control, and Severe-Control).
 
For Part 2 for each day (as appropriate), using GLM procedures in SAS, ANOVA will be performed on untransformed K_{el} and $T_{1/2\ el}$ and on ln-transformed AUC_{0-12}, AUC_{0-24}, AUC_{0-t}, AUC_{0-inf}, C_{max}, and C_{trough} at the alpha level of 0.05 for nalbuphine and metabolite(s).
 
For Part 2 of the study, a repeated measures analysis will be carried out on ln-transformed pre-morning and evening dose concentrations (when applicable) (on Days 2, 3, 5, 6, 8, 9, 11, 12, and 13) to determine attainment of steady state.
 
Within each group, dose proportionality will be assessed by a visual assessment of the individual and mean nalbuphine PK parameters. A power model analysis may also be performed to evaluate the doses-exposure, if warranted.
 
For the WI-NRS variables, post-dose scores will be assessed as an increment or decrement relative to the pre-dose baseline values. Each time point will be evaluated separately, relative to the baseline (pre-dose) value. Pair-wise comparisons among the groups will be made.
 
Review of interim safety analyses will be performed between cohorts or groups. Interim PK analyses may be performed between cohorts or groups if requested or warranted.
 
A complete description of the statistical analyses to be performed with the safety and tolerability data, as well as PK parameters will be presented in a Statistical Analysis Plan, which will be finalized prior to database lock.

--	---

3. List of Abbreviations

AE	Adverse event
ALT	Alanine aminotransferase
ANOVA	Analysis of variance
AST	Aspartate aminotransferase
AUC	Area under the curve
BMI	Body mass index
BUN	Blood urea nitrogen
CI	Confidence interval
CFR	Code of Federal Regulations
C _{max}	Maximum plasma concentration
C _{trough}	Last plasma concentration
COC	Combined oral contraceptives
CONMED	Concomitant medication
CP	Child-Pugh classification
CRF	Case Report Form
CV	Coefficient of variation
CYP	Cytochrome P450
DDI	Drug-drug interaction
DLT	Dose-limiting toxicity
ECG	Electrocardiogram
eGFR	Estimated glomerular filtration rate
FDA	Food and Drug Administration

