Based on the overall safety and tolerability observed in the subjects with mild and moderate impairment, at the completion of all doses tested, it will be determined by the Safety Committee whether or not it is safe to proceed with dosing for the first 2 subjects with severe Impairment. After review of the safety and tolerability for the first 2 severe subjects dosed at 27 mg, it will be determined whether or not to complete that dose level for the remaining severe subjects.

At the completion of all subjects dosed in the cohort, there will be an evaluation of safety and tolerability to determine whether to proceed to the next dose level for this group.

The Safety Committee will be composed of at least the Investigators and one medically qualified Sponsor representative. Some adjustments to the currently outlined doses and/or dosing regimen may be implemented by the Safety Committee, but the dose to be administered in a given dose cohort will not exceed the one currently outlined in the protocol.

Drug administration in Part 2 of the study (MAD) may be initiated following satisfactory review of the safety and tolerability data from Groups 1 and 2 (mild and moderate impairment) from Part 1 of the study (SAD) by the Safety Committee. Depending on safety and tolerability as well as on available PK data, the dose escalation scheme may be modified such that intermediate dose levels are administered. The dosage regimen (once daily versus twice daily) will be confirmed following review of PK data from Part 1 of the study (SAD).

If in the judgement of the Safety Committee the Part 1 PK data demonstrates dose linearity across the dose range in both the mild and moderate hepatic impairment subjects (Group 1 and Group 2 subjects), such that PK modeling can be predictive of steady state dosing levels, a decision may be made to end the study without conducting Part 2 of the study

In Part 2 of the study (MAD), subjects will receive a single 27 mg dose in the morning of Day 1. Starting on Day 2, doses will be subsequently escalated for each subject to twice daily, 12 hours apart, 27 mg, 54 mg, 108 mg, and 162 mg over 13 days. On the last treatment day, (Day 13), subjects will receive a single 162 mg dose in the morning. Subjects will remain at each dose level for 2-3 days (minimum 5 consecutive doses) with dose escalation predicated on tolerability of the prior dose (See Section [9.14.4](#) for dose escalation stopping rules).

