9.8 PK Sample Collection and Processing

9.8.1 Plasma Samples

Part 1 (SAD) – Cohorts 1 to 5

A total of 11 blood samples will be collected: at pre-dose and 1.5, 3, 5, 7, 9, 12, 24, 36, 48, and 72 hours post-dose (up to 3 mL for each sampling time).

For Part 1, the total volume of blood including that collected for eligibility and safety purposes should not exceed 160 mL for each dose level.

Part 2 (MAD) – Cohort 6

On Day 1: a total of 10 blood samples will be collected for quantitation of nalbuphine and metabolite(s) in plasma: pre-dose and 1.5, 3, 4, 5, 6, 7, 9, 12, and 24 hours post-dose (up to 3 mL for each sampling time).

On Days 4, 7, and 10, a total of 9 blood samples will be collected: at pre-morning dose and 1.5, 3, 4, 5, 6, 7, 9, and 12 hours post-dose (prior to the evening dose administration) (up to 3 mL for each sampling time).

On Day 13, a total of 12 blood samples will be collected: at pre-dose and 1.5, 3, 5, 7, 9, 12, 24, 36, 48, 72, and 96 hours post-last dose (up to 3 mL for each sampling time).

Trough blood samples will be collected on Days 2, 3, 5, 6, 8, 9, 11, 12, and 13 prior to the morning and evening (if applicable) dose administrations (up to 3 mL for each sampling time). Pre-dose samples for the evaluation of steady state attainment will be collected at approximately the same time each day and within 10 minutes prior to dosing.

The 12-hour and 24-hour (when applicable) post-morning Day 1, 4, 7, 10, and Day 13 dose samples will be collected within 10 minutes of the nominal time. For timepoints up to 1 hour, a window of ± 1 minute will be allowed for blood collection. From 1.5 hour to 2 hours, a window of ± 2 minutes will be allowed. From 2.5 hours to 12 hours, the time window will be ± 5 minutes and for 16 hours to 72 hours, the time window will be ± 10 minutes. Actual post-dose sampling times will be used for PK analyses.

Unless otherwise specified or for subject safety, when blood draws and other procedures coincide, blood draws will have precedence. A saline intravenous catheter may be used for blood collection to avoid multiple skin punctures, when appropriate. Otherwise, blood samples will be collected by direct venipuncture.

For Part 2, the total volume of blood including that collected for eligibility and safety purposes should not exceed 358 mL for the whole study.

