Also, for Part 2 of the study, a repeated measures analysis of variance (RMA) will be carried out on ln-transformed pre-morning and evening dose (when applicable) concentrations (Days 2, 3, 5, 6, 8, 9, 11, 12, and 13) to determine attainment of steady state.

Within each group, dose proportionality will be assessed by a visual assessment of the individual and mean nalbuphine PK parameters. A power model analysis may also be performed to evaluate the doses-exposure, if warranted.

In the event that hepatic impairment has a clinically relevant effect on nalbuphine and metabolite(s) PK, the relationship between measures of hepatic function and appropriate PK parameters (eg CL/F , AUC_{0-12} , AUC_{0-24} , AUC_{0-t} , AUC_{0-inf} , AUC_{0-t} , C_{trough} , and C_{max}) will be determined by a linear or non-linear regression.

Study results including the graphical description and the relationships between hepatic function and relevant PK parameters will be used to elaborate specific dosing recommendations if deemed clinically relevant.

For the WI-NRS variables, post-dose scores will be assessed as an increase or decrease relative to the pre-dose values. Each time point will be evaluated separately, relative to the baseline (pre-dose). Pair-wise comparisons among the group will be made if applicable.

Review of interim safety analyses will be performed between cohorts or groups. Interim PK analyses could be performed between cohorts or groups if requested or warranted.

A complete description of the statistical analyses to be performed with the safety and tolerability data, as well as PK parameters will be presented in the SAP, which will be finalized prior to database lock. Additional statistical analysis may be performed and will be described in the SAP.

13. Informed Consent

Potential subjects must provide written consent to participate after the nature, scope, and possible consequences of study have been explained in a form understandable to them.

An ICF that includes information about the study will be prepared and given to the subject. This document will contain all the elements required by the ICH E6 Guideline for GCP and any additional elements required by local regulations. The document must be in a language understandable to the subject and must specify who informed the potential subject. Where required by local law, the person who informs the potential subject must be a physician.

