## 8.6 Steady-State Attainment

For Part 2 of the study, a repeated measures analysis of variance (RMA) will be carried out on ln-transformed pre-morning and evening dose (when applicable) concentrations (Days 2, 3, 5, 6, 8, 9, 11, 12, and 13) to determine attainment of steady state.

Repeated measures analysis of the last three pre-dose concentrations (Ln transformed) will be statistically analyzed using General Linear Model (PROC GLM) of SAS® version 9.4 software.

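### The steady-state test takes morning and evening pre-dose samples together with no time-of-day term, so a stable morning/evening trough difference cannot be told apart from failure to reach steady state

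*Protocol*

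**What the plan says.** The protocol describes one steady-state analysis for Part 2. The synopsis (Statistical Analyses) says "a repeated measures analysis will be carried out on ln-transformed pre-morning and evening dose concentrations". Section 12.3 repeats this as an analysis that "will be carried out on ln-transformed pre-morning and evening dose (when applicable) concentrations", on "Days 2, 3, 5, 6, 8, 9, 11, 12, and 13) to determine attainment of steady state".

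SAP Section 8.6 carries the same sentence and adds the subset and procedure: "Repeated measures analysis of the last three pre-dose concentrations (Ln transformed) will be statistically analyzed using General Linear Model".

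On sampling, Protocol Section 9.8.1 states: "Trough blood samples will be collected on Days 2, 3, 5, 6, 8, 9, 11, 12, and 13 prior to the morning and evening" doses. The samples are to be "collected at approximately the same time each day and within 10 minutes prior to dosing". The titration table in Section 9.4 gives 162 mg from the evening of Day 10. On the last treatment day "subjects will receive a single 162 mg dose in the morning", so Day 13 has no pre-evening sample.

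Neither document gives a morning/evening factor, separate morning and evening series, a contrast, an alpha or a decision rule for this test. The model is not written out.

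**The concern.** On a twice-daily regimen, steady state means that the 24-hour profile repeats from day to day. It does not require the trough before the evening dose to equal the trough before the morning dose. One follows the daytime interval and the other the overnight interval.

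In a morning-evening-morning sequence with no time-of-day term, a constant difference between the two kinds of trough appears as a time effect. A significant result could then mean continuing accumulation or only a stable daily pattern, and the analysis as described could not say which. What is at stake is the interpretation of the one formal check on steady state in Part 2.

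**Working it through.** **Which samples are tested.** Day 13 has only a morning dose, so the listed days give 8 × 2 + 1 = 17 pre-dose samples under the twice-daily schedule. The last three in time are Day 12 AM, Day 12 PM and Day 13 AM. Each follows a 162 mg dose given 12 hours earlier.

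**No figure to reproduce.** The documents give no power or error rate for this test.

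**Inputs.**
- Subjects: 6-8 mild and 6-8 moderate (synopsis, Cohort 6). That is 12-16 if the groups are analysed together (G = 2) and 6-8 if one group is analysed alone (G = 1).
- Alpha: assumed 0.05, the level stated for the other Part 2 ANOVAs.
- Within-subject SD of ln trough: assumed 0.20 to 0.30. Protocol Section 5.1.1.2 says only that intra-subject variability is lower than inter-subject variability.
- Evening/morning trough ratio R: assumed 1.1 or 1.2.

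**Formula.** At true steady state the three means on the ln scale are (0, d, 0), with d = ln R. Their sum of squares about the mean is (2/3)d². The 2-df time effect therefore follows a noncentral F with df 2 and 2(n − G), and noncentrality λ = n × (2/3) × d² / SD².

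Example: n = 12, G = 2, R = 1.2, SD 0.20. Here d = 0.1823, λ = 12 × 0.6667 × 0.03324 / 0.04 = 6.65, and the critical F(2, 20) is 3.49. The rejection probability is 0.56.

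| n (G) | R = 1.1, SD 0.20 | R = 1.1, SD 0.30 | R = 1.2, SD 0.20 | R = 1.2, SD 0.30 |
|---|---|---|---|---|
| 6 (1) | 10% | 7% | 27% | 14% |
| 8 (1) | 13% | 8% | 38% | 19% |
| 12 (2) | 18% | 11% | 56% | 28% |
| 16 (2) | 24% | 13% | 71% | 37% |

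With R = 1 the rate is the nominal 5%. A simulation with 12 subjects in a single group, a CV of 20% and 20,000 runs gave 4.9% at R = 1 and 57% at R = 1.2.

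**Same-clock-time comparison.** In the same simulation, Day 13 AM against Day 12 AM rejected in 5.0% of runs at R = 1.0, 1.2 and 1.3.

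**How close each 162 mg trough is to plateau.** This uses superposition of the titration table with the half-life range of 6.6 to 9.6 h in Section 5.1.1.2, which comes from subjects with normal renal function. Percentages are of the 162 mg plateau.

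| Trough | Half-life 6.6 h | Half-life 9.6 h |
|---|---|---|
| Day 11 AM | 91% | 86% |
| Day 11 PM | 97% | 94% |
| Day 12 AM | 99% | 98% |
| Day 12 PM | above 99% | 99% |
| Day 13 AM | above 99% | above 99% |

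The expected Day 12 PM / Day 11 PM ratio is 0.998/0.973 = 1.03 to 0.990/0.941 = 1.05. For Day 13 AM / Day 12 AM it is 0.999/0.992 = 1.01 to 0.996/0.975 = 1.02. The morning pair is the cleaner comparison.

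**The case against.** The strongest reply is that no document shows morning and evening troughs to differ. The three preceding doses are all 162 mg. Section 9.7.1 applies the same 2-hour food rule to both daily doses on Days 2 to 12. The reported food effect (Section 5.1.1.2) is on Cmax, with AUC and Tmax unchanged. This stands: the size of the problem is unknown, and large rejection rates hold only under assumed differences.

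The same-time-each-day rule in Section 9.8.1 would also be compatible with a same-clock-time analysis. That is true, but it governs collection. It does not separate the two series in the analysis, and SAP Section 8.6 does not either. With the model not written out, three consecutive samples is the plain reading rather than a literal statement.

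Three stronger readings are tempting, and the documents do not support them:
- **Posture as a cause.** The restriction "for 4 hours after morning drug administration" applies on Days 1, 4, 7, 10 and 13. The tested troughs follow the Day 11 evening and both Day 12 doses, so none of those doses is covered.
- **Masking a real rise.** The Day 12 AM to Day 13 AM contrast (−1, 0, 1) is orthogonal to the morning/evening contrast (1, −2, 1). For a rise b the time sum of squares per subject is at least b²/2, whatever the evening value. A morning/evening gap cannot cancel that rise.
- **Downstream decisions.** Nothing makes the Day 13 parameters conditional on this test. Once- or twice-daily dosing in Part 2 is confirmed from Part 1 data (Section 9.4).

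**Conclusion.** The point holds as a specification weakness with a cheap remedy. As described, the test cannot distinguish a stable morning/evening trough difference from non-attainment of steady state.

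Its practical size cannot be fixed from the documents. Under the assumptions above, false rejection is little above nominal for a 10% difference in a single group (7-13%). It becomes material for a 20% difference in the combined groups (28-71%). If the troughs do not differ, there is no inflation.

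The point applies only if Part 2 is conducted and remains twice daily. Under once-daily morning dosing every pre-dose sample would be a morning sample. A reader might infer that Part 2 exposure results or the dosing-frequency choice would be invalidated, but the documents tie neither to this test.

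**What to change.** In SAP Section 8.6 and Protocol Section 12.3, write out the model and the criterion, and compare like with like:

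- Either compare pre-dose concentrations at the same clock time, or add morning/evening as a within-subject term and assess day-to-day change within it.
- At 162 mg, make Day 13 AM / Day 12 AM the main comparison, reported as a geometric mean ratio with a 90% CI.
- Day 12 PM / Day 11 PM may be shown as supportive. State that Day 11 PM follows only two 162 mg doses and is expected at about 94-97% of plateau for half-lives of 9.6 to 6.6 h, so a ratio of about 1.03 to 1.05 is expected.
- Avoid a three-morning test on Days 11 to 13 without comment, because Day 11 AM follows a single 162 mg dose (86-91% of plateau).

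All samples are already scheduled. The cost is a few sentences and fewer time points or degrees of freedom in the test.

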4.1 Schedule of Events – Part 1 (Single Ascending Dose)

Procedure	Screening (Day -28 to Day -2)	Cohorts 1 to 5 Each Dose Level ^a			Study Exit D4 (72 h) or Early Termination
		D-1	D1	D2 (24 h) D3 (48 h)	
Informed consent	X				
Review inclusion/exclusion	X	X	X		
Demographic data	X				
Medical and medication histories	X				
Review and monitoring of AEs and concomitant medications	X	X	X	X	X
Physical examination ^b	X	X			X
Height, weight, and BMI	X				
Vital signs ^c	X	X	X	X	X
Body temperature	X	X			X
12-lead ECG ^d	X	X	X	X	X
Pulse oximetry ^c	X	X	X	X	X
Clinical chemistry ^f	X	X			X
Hematology ^f	X	X			X
Coagulation (PT, aPTT, and INR) ^f	X	X			X
HIV and hepatitis	X				
Urinalysis ^f	X	X			X
Urine alcohol and drug screen	X	X			
Urine and serum pregnancy test (as applicable)	X	X			X
Confinement ^g		X	X	X	
Drug administration			X		
PK samples ^h			X	X	X

- Subjects in Cohorts 1 to 4, Part 1 of study, can participate in all 4 dose levels. There will be a washout period of at least 7 days between drug administration at each dose level and between each part of the study. The same procedures will be followed for all dose levels. Screening procedures are required only for naïve subjects in Cohorts 2-4 who have not previously been screened.
- A complete physical examination will be performed at screening. A brief physical examination will be performed on Day -1 and Day 4. The complete physical examination will include at least the following components: head, eyes, ears, nose, throat (HEENT), neck, lungs, abdomen, skin, cardiovascular and musculoskeletal evaluation, and general neurological examination.
- Blood pressure, heart rate, and respiratory rate: at screening, in the morning of Day -1, pre-dose, approximately 1, 2, 4, 6, 8, 12, 24, and 48 hours post-dose, and Day 4.
- 12-lead ECG: at screening, in the morning of Day -1, pre-dose, approximately 1, 2, 4, 6, 8, 12, 24, and 48 hours post-dose, and on Day 4.

-
- e. Oxygen saturation via pulse oximetry will be measured at screening. Baseline continuous pulse oximetry will be measured during the nighttime of Day -1 (minimum of 8 hours prior to first dose administration). Following the dose and throughout study conduct, oxygen saturation will be measured via pulse oximetry at pre-dose and 1.5, 4.5, and 8 hours post-dose. Pulse oximetry measurements may be collected within 10 min before or after the specified time point. Oxygen saturation will be monitored via pulse continuous oximetry beginning at bedtime and continuing overnight until waking time from Day 1 to end of confinement with oxygen saturation measurements specifically recorded at approximately midnight and 4 am.
 - f. Laboratory assessments (ie, clinical chemistry, hematology, coagulation, and urinalysis) will be done at screening, in the morning of Day -1, and Day 4 following a fasting period of at least 8 hours.
 - g. Subjects in Cohorts 1 to 4 will be confined from the morning of Day -1 until discharge on Day 4 (after the 72-hour post-dose blood draw). Cohort 5 subjects will be confined from the morning of Day -1 until discharge on Day 3 (after the 48-hour post- dose blood draw), and will come back for the Day 4 procedures.
 - h. PK blood samples: A total of 11 blood samples will be collected: at pre-dose and 1.5, 3, 5, 7, 9, 12, 24, 36, 48, and 72 hours post-dose.

4.2 Schedule of Events – Part 2 (Multiple Ascending Dose)

Procedure	Screening (Day -28 to Day -2)	Cohort 6												Dis-charge D16	Study Exit D17	Early Termination ⁱ
		D-1	D1	D2 D3	D4	D5 D6	D7	D8 D9	D10	D11 D12	D13	D14 D15				
Informed consent	X															
Review inclusion/ exclusion	X	X	X													
Demographic data	X															
Medical and medication histories	X															
Review and monitoring of AEs and concomitant medications	X	X	X	X	X	X	X	X	X	X	X	X	X	X	X	X
Physical examination ^a	X	X												X		X
Height, weight, and BMI	X															
Vital signs ^b	X	X	X	X	X	X	X	X	X	X	X	X	X	X		X
Body temperature	X	X												X		X
12-lead ECG ^c	X	X	X	X	X	X	X	X	X	X	X	X	X	X		X
Pulse oximetry ^d	X	X	X	X	X	X	X	X	X	X	X	X	X	X		X
Clinical chemistry ^e	X	X				X			X					X		X
Hematology ^e	X	X				X			X					X		X
Coagulation (PT, aPTT, and INR) ^e	X	X												X		X
HIV and hepatitis	X															
Urinalysis ^e	X	X												X		X
WI-NRS ^f	X	X	X	X	X	X	X	X	X	X	X	X	X	X		X
Urine alcohol and drug screen	X	X														
Urine and serum pregnancy test (as applicable)	X	X												X		X
Confinement ^g		X	X	X	X	X	X	X	X	X	X	X				
Drug administration 27 mg qd			X													
Drug administration 27mg bid				X												
Drug administration 27 mg (morning) and 54 mg (evening)					X											
Drug administration 54 mg bid						X										

Procedure	Screening (Day -28 to Day -2)	Cohort 6												Dis-charge D16	Study Exit D17	Early Termination ⁱ
		D-1	D1	D2 D3	D4	D5 D6	D7	D8 D9	D10	D11 D12	D13	D14 D15				
Drug administration 54 mg (morning) and 108 mg (evening)							X									
Drug administration 108 mg bid								X								
Drug administration 108 mg (morning) and 162 mg (evening)									X							
Drug administration 162 mg bid										X						
Drug administration 162 mg qd											X					
PK samples ^h			X	X	X	X	X	X	X	X	X	X	X	X	X	X

- A complete physical examination will be performed at screening. A brief physical examination will be performed on Day -1 and Day 16. The complete physical examination will include at least the following components: head, eyes, ears, nose, throat (HEENT), neck, lungs, abdomen, skin, cardiovascular and musculoskeletal evaluation, and general neurological examination.
- Blood pressure, heart rate, and respiratory rate: at screening, in the morning of Day -1, pre-morning dose every day (Days 1 to 13), approximately 1, 2, 4, 6, 8, and 12 hours post-morning dose on Day 1 and Day 13, approximately 2 and 6 hours post-morning dose on Days 2 to 12, and once on Days 14, 15, and 16.
- 12-lead ECG: at screening, in the morning of Day -1, pre-morning dose every day (Days 1 to 13), approximately 1, 2, 4, 6, 8, and 12 hours post-morning dose on Day 1 and Day 13, and once on Days 14, 15, and 16.
- Oxygen saturation via pulse oximetry will be measured at screening. Baseline continuous pulse oximetry will be measured during the nighttime of Day -1 (minimum of 8 hours prior to first dose administration). Following the first dose and throughout study conduct, oxygen saturation will be measured via pulse oximetry at pre-morning dose, at 1.5, 4.5, and 8 hours following the morning dose, and at 2 hours following the evening dose. Pulse oximetry measurements may be collected within 10 min before or after the specified time point. Oxygen saturation will be monitored via pulse continuous oximetry beginning at bedtime and continuing overnight until waking time from Day 1 to end of confinement with oxygen saturation measurements specifically recorded at approximately midnight and 4 am.
- Laboratory assessments (ie, clinical chemistry, hematology, coagulation, and urinalysis) will be done at screening, in the morning of Day -1, and Day 16 following a fasting period of at least 8 hours. Clinical chemistry and hematology also on Day 5 and Day 10.
- Cohort 6 subjects will complete both of the two WI-NRS forms (the “Nighttime Itch” and the “Daytime Itch”) at the same time during the screening visit, and the average will be taken to determine the baseline severity. WI-NRS will be subsequently performed on a daily basis, from Day -1 to Day 16, to be collected twice per day: once within an hour (+/- 1 hour) of completing their morning and evening meals, if applicable. Subjects will fill in the “Nighttime Itch” form in the morning and the “Daytime Itch” form in the evening.
- Cohort 6 subjects will be confined from the morning of Day -1 until discharge on Day 16 (after the 72-hour post-last dose blood draw). Subjects will come back on Day 17 for the subsequent final blood draw (96-hour post-last dose blood draw) at the Study Exit visit.
- PK blood samples:
 - On Day 1: a total of 10 blood samples will be collected for quantitation of nalbuphine and metabolite(s) in plasma: at pre-dose and 1.5, 3, 4, 5, 6, 7, 9, 12, and 24 hours post-dose.
 - On Days 4, 7, and 10: a total of 9 blood samples will be collected; at pre-morning dose and at 1.5, 3, 4, 5, 6, 7, 9, and 12 hours post-dose (prior to the evening dose administration).
 - On Day 13: a total of 12 blood samples will be collected: at pre-dose and 1.5, 3, 5, 7, 9, 12, 24, 36, 48, 72, and 96 hours post-last dose.

Procedure	Screening (Day -28 to Day -2)	Cohort 6												Dis- charge D16	Study Exit D17	Early Termination ⁱ
		D-1	D1	D2 D3	D4	D5 D6	D7	D8 D9	D10	D11 D12	D13	D14 D15				

- Trough blood samples will be collected on Days 2, 3, 5, 6, 8, 9, 11, 12, and 13, prior to the morning and evening dose administrations (when applicable).
- i. In Part 2 of the study, Early Termination procedures are only applicable to subjects who discontinue study drug for reasons other than those related to DLT. In the case that a subject experiences a DLT or a DLT dose is confirmed in 2 subjects during Part 2, post last-dose study procedures will be performed as laid out in the DLT Follow-Up Period (see Section [4.3](#) schedule of events and Section [9.11.1](#) procedures).

